**3. Protocol Personnel**

Including the PI, list all key personnel (each individual involved in the design and conduct of this protocol including recruitment, informed consent, analysis of the data, and reporting of the results). Complete either the UAB (3.a.) or non-UAB (3.b) table, as applicable. Use the checkboxes to show each person's role, whether the investigator has financial interests as defined by the UAB CIRB, and briefly describe the individual's responsibilities for the research and qualifications to perform those responsibilities. Insert additional rows as needed.

**FDA:** For studies involving investigational drugs, list all investigators who will be listed on FDA Form 1572 and include a copy of the 1572. Send the IRB a copy of Form 1572 any time you update the form with the FDA.

**c. Do the investigators listed above include any students using this research for their thesis or dissertation?**

- No, continue with Item 3.d.  
 Yes, complete the following

Student Name	Thesis/Dissertation Title

**d. Is the principal investigator a student, fellow, or resident?**  Yes  No

**If Yes**, complete items below and obtain signature of faculty advisor or supervisor:

Supervisor's Name: \_\_\_\_\_  
 Degree(s) / Job Title: \_\_\_\_\_  
 Additional Qualifications pertinent to the study: \_\_\_\_\_  
 Telephone: \_\_\_\_\_  
 E-Mail: \_\_\_\_\_

**Signature:** \_\_\_\_\_

- e. Describe the principal investigator's activities related to this protocol and provisions made by the PI to devote sufficient time to conduct the protocol: **[name] will show whether or not the Aerodentis device reduces orthodontic treatment time by comparing the time for standard orthodontic treatment to the actual time observed with Aerodentis use.**
- f. Is medical supervision required for this research? Yes No  
**If Yes**, who will provide the supervision?  
 PI will provide -OR- Name: \_\_\_\_\_ Telephone: \_\_\_\_\_  
 If other than PI, obtain signature of person providing medical supervision:  
 Signature \_\_\_\_\_
- g. Describe the process that ensures that all persons assisting with the research are adequately informed about the protocol and their research-related duties and functions: **[name] has had extensive training and experience in orthodontic research. [name] has been in frequent contact with members of the Aerodentis team and has helped in writing the proposal for this study. He has kept in touch through weekly email correspondence and multiple conference calls. [name] has also visited Aerodentis headquarters in Israel to learn about their orthodontic system. [name] will train all UAB team members included in research. [name] and co-investigators will assess the efficacy and safety of the Aerodentis system for orthodontic tooth movement and alignment.**

#### 4. Funding

- Is this study funded? Yes No
- If No**, specify that costs of the study will be covered by funds from the UAB department or other source named: \_\_\_\_\_
- If Yes**, attach one copy of completed application or request for funding sent to sponsor, and complete a-d.
- a. Title of Grant or Contract: **Assessment of the Efficacy of Orthodontic Tooth Movement Using the Aerodentis System**
- b. PI of Grant or Contract: **[name] [name]**
- c. Office of Sponsored Programs Proposal Number: **000513374**  
 (or enter "Pending" and provide upon receipt from OSP)
- d. Sponsor, Funding Route (check and describe all that apply):
- Gov't Agency or Agencies—Agency name(s): \_\_\_\_\_
    - Department of Defense (DoD): Identify DoD component: \_\_\_\_\_
    - Department of Energy (DOE)
    - Department of Justice (DOJ)
    - Department of Education
  - NIH Coop. Group Trial—Group name: \_\_\_\_\_
  - Private Nonprofit (e.g., Foundation)—Name: \_\_\_\_\_
  - Industry, investigator-initiated—Name: **Dror Ortho-Design Ltd.** Describe the funding arrangement: **We are utilizing a UAB Clinical Trials Agreement between the Board of Trustees and Dror Ortho-Design Ltd.**  
*Note. Western IRB reviews industry-sponsored protocols unless the investigator initiated the research, or the study qualifies for expedited review or involves gene therapy.*
  - UAB Departmental/Division Funds—Specify: \_\_\_\_\_

#### 5. Locations Involved

- a. Describe the facilities available for the conduct of the research. For research on UAB campus, include building names and room numbers: UAB School of Dentistry, Department of Orthodontics Clinic, SDB 305
- b. Indicate all "performance sites" that will provide space, services, facilities, potential or actual participants, or other support for this protocol.
- The Kirklin Clinic (TKC)
  - University of Alabama Hospital (UAHosp)
  - The Children's Hospital of Alabama (TCHA)
  - Callahan Eye Foundation Hospital (CEFH)
  - UAB Highlands
  - Jefferson County Dept. of Health (JCDH)
  - Birmingham Veterans Affairs Medical Center (BVAMC)
  - General Clinical Research Center (GCRC)—inpatient
  - General Clinical Research Center (GCRC)—outpatient
  - General Clinical Research Center (GCRC) at The Kirklin Clinic (TKC)
  - Other (i.e., Any performance site not listed above, including those covered by subcontracts related to this protocol)—Describe: \_\_\_\_\_
- c. Is this study a clinical trial requiring clinical services at one of the performance sites listed in Item b above?  Yes  No  
**If Yes**, Fiscal Approval Process (FAP)-designated units complete a FAP submission and send to [[contact]](mailto:[contact]). For more on the UAB FAP, see [www.uab.edu/osp/clinical-billing-review](http://www.uab.edu/osp/clinical-billing-review).
- d. Is this a field study?  Yes  No  
**If Yes**, describe the community and include information about how the community will be involved in the design, implementation and analysis of the research. This would include focus groups, training local facilitators/community health advisors: \_\_\_\_\_
- e. Is the study to be undertaken within a school, business, or other institution that does not have an institutional review board?  Yes  No  
**If Yes**, attach a statement of any contacts with and approvals from the appropriate institution officials.  
*Note. Documentation of all such approvals must be received by the UAB OIRB before IRB approval will be issued.*
- f. Has this protocol or project been reviewed by another IRB, similar review board, or departmental review committee(s) that authorizes the use of its patient populations?  Yes  No  
**If Yes**, provide name of the review board(s): \_\_\_\_\_ and for each board listed, enter either the date of latest approval(s) or "PENDING": \_\_\_\_\_ or reasons not approved: \_\_\_\_\_. *If this protocol is subsequently rejected or disapproved by another review board, the UAB IRB must be notified promptly. Attach copies of approvals/disapprovals.*
- g. Will any of the participants be from the Birmingham Veterans Affairs Medical Center?  Yes  No

**If Yes**, attach VA IRB approval or notification from the VA Research and Development Department that the study has been submitted to the VA IRB for review.

- h.** Will the study be conducted at or recruit participants from the Jefferson County Department of Public Health (JCDH)?  Yes  No

**If Yes**, attach notification that the protocol has been approved by JCDH or the Alabama Department of Public Health IRB.

## 6. Multi-Site Studies

- a.** Is the investigator the lead investigator of a multi-site study?  Yes  No

- b.** Is UAB a coordinating site in a multi-site study?  Yes  No

- c.** If you answered **Yes** to *a* or *b*, describe the management of information obtained in multi-site research that might be relevant to the protection of participants.

Include, at a minimum, the following items:

- IRB approvals from other sites
- Unanticipated problems involving risks to participants or others. (For example, if there is an unanticipated problem involving risks to participants or others, which site is responsible for reporting it?)
- Interim results.
- Protocol modifications.

- 7. Drugs:** Will any drugs or supplements be used/studied in this protocol?  Yes  No  
**If Yes**, attach the [Drug Review Sheet](#).

- 8. Devices:** Will any devices be studied in this protocol or used for a purpose other than for which they were approved by the FDA?  Yes  No  
**If Yes**, attach the [Device Review Sheet](#).

## 9. Special Approvals

- a.** Does this project involve the use of radioisotopes?  Yes  No  
**If Yes**, attach documentation of approval from the Radiation Safety Division.

- b.** Does this project include patients with contagious infections (e.g., mumps, measles, chickenpox, TB, meningitis)?  Yes  No  
**If Yes**, attach documentation of approval from Chairman of the Infection Control Committee of the appropriate facilities.

- c.** Does this project involve obtaining remnant biopsy or surgical material from the Department of Pathology or any other source?  Yes  No  
**If Yes**, attach documentation of approval from the entity or individual providing the materials (e.g., the [UAB Division of Anatomic Pathology Release of Pathologic Materials](#)).

- d.** Does this project require obtaining any remnant clinical laboratory specimens, body fluids, or microbiological isolates from the Department of Pathology or any other source?  Yes  No  
**If Yes**, attach documentation of approval from the entity or individual providing the materials (e.g., the [UAB Division of Laboratory Medicine Release of Pathologic Materials](#)).

- e.** Does this project use stored (existing) specimens from a repository?  Yes  No

**If Yes**, attach documentation of approval for use of specimens, and describe how existing specimens are labeled: \_\_\_\_\_

## 10. Use of Specimens

Does this project involve collecting specimens from participants and storing them for future research?  Yes  No

**If Yes**, complete a-h. If no, skip to Item 11

a. How will specimens be obtained, processed, distributed, and stored?  
\_\_\_\_\_

b. How will specimens be labeled (e.g., unique identifier, medical record number, Social Security number, name, date of birth)?  
\_\_\_\_\_

c. How will clinical data associated with the specimens be collected and stored?  
\_\_\_\_\_

d. What participant-identifying information will be collected and linked to the specimens?  
\_\_\_\_\_

e. What steps will be taken to maximize the confidentiality of linked identifiers? For example, procedures could include using a password-protected computer database to link identifiers, with limited personnel knowledgeable of the password, or coded identifiers released without the ability to link to clinical data (also called "stripped" or "anonymized" specimens).  
\_\_\_\_\_

f. Will specimens be shared with other investigators in the future?  Yes  No  
**If Yes**, what identifiers, clinical information and demographic information will be shared; or will the specimens be stripped of identifiers (i.e., anonymized)? Also **if yes**, outline your procedure for assuring IRB approval for release and use prior to release of specimens.  
\_\_\_\_\_

*Note. Investigators who receive and/or use these specimens must document approval from the appropriate IRB(s) before the specimens may be released.*

g. Will biological samples be stored for future use?  Yes  No  
**If Yes**, indicate whether they will be used for the disease under study in this protocol or research on other diseases.  
\_\_\_\_\_

h. Is genetic testing planned?  Yes  No  
**If Yes**, describe the planned testing here and see "DNA/Genetic Testing" in the Guidebook for consent requirements.  
\_\_\_\_\_

## 11. Gene Therapy

Does this project involve gene therapy or administering recombinant materials to humans?  Yes  No

**If Yes**, submit the [Gene Therapy Project Review Panel Report](#) -OR- If this is a vaccine trial that is exempt from the NIH Guidelines For Research Involving

## 12. HIPAA Privacy and Security

Will the PI or others obtain, review, or make other use of participants' "personal health information" (i.e., information, whether oral or recorded in any form or medium that (a) is created or received by a health care provider and (b) relates to past, present, or future physical or mental health or condition of an individual; or provision of health care; or payment for provision of health care)? Yes No

**If Yes**, complete a-e as described.

**a.** Will the data/information be stored or managed electronically (on a computer)? Yes No

**b.** Is the principal investigator requesting that the UAB IRB waive patient HIPAA authorization from another institution or entity (e.g., insurance company, collaborating institution). Yes No

**If Yes**, attach copy of privacy notices from institution/entity, and provide the name of institution/entity: \_\_\_\_\_

**c.** Indicate which, if any, of the listed entities below would provide information or maintain health information collected for this protocol and/or where health information that been collected will be stored/maintained.

- The Kirklin Clinic
- University of Alabama Hospital
- The Children's Hospital of Alabama
- Callahan Eye Foundation Hospital
- UAB Highlands
- Jefferson County Department of Health
- School of Dentistry
- School of Health Professions
- School of Medicine
- School of Nursing
- School of Optometry
- University of Alabama Health Services Foundation
- UAB Health Centers
- Viva Health
- Ophthalmology Services Foundation
- Valley Foundation
- Medical West - UAB Health System Affiliate
- Health System Information Systems:*
- HealthQuest
- Cerner Millennium (Lab, Radiology, UED, Surgery)
- EMMI - Master Member Index
- Horizon - IPV (IVR/CDA/CRIS)
- CareFlow Net
- Eclipsys (PIN)
- IMPACT
- None—**If None, skip to Item 13.**

d. Indicate which of the listed identifiers would be associated/linked with the protected health information (PHI) used for this protocol.

- Names
- Geographic subdivisions smaller than a State
- Elements of dates (except year) related to an individual
- Telephone numbers
- Fax numbers
- Email addresses
- Social security numbers
- Medical record numbers
- Health plan beneficiary numbers
- Account numbers
- Certificate/license numbers
- Vehicle identifiers and serial numbers
- Device identifiers and serial numbers
- Biometric identifiers
- Web universal resource locators (URLs)
- Internet protocol address numbers
- Full-face photographic images
- Any other unique identifying number—Describe: \_\_\_\_\_

*Note. Codes are not identifying as long as the researcher cannot link the data to an individual*

None—**If None, skip to Item 13.**

e. Choose one plan to describe your use of the personal health information:

- The data collected meet the specifications for a "limited data set"  
—Attach [Data Use Agreement](#) or Business Associate Agreement
- Research staff will obtain authorization from each patient to use the information  
—Attach [Patient Authorization](#) form, complete except for patient name and IRB protocol number
- PI requests Waiver of Patient Authorization to use the information  
—Attach [Waiver of Authorization and Informed Consent](#) form

### PROPOSED RESEARCH

- The IRB will not accept grant applications and/or sponsor's protocols in lieu of the items as outlined below.
- Do not separate responses from items. Instead, insert your response to each item below the item, keeping the information in the order of this form.
- Number each page of the Human Subjects Protocol (i.e., Page X of Y).

### 13. Purpose—in nontechnical, lay language

Summarize the purpose and objectives of this protocol, including any related projects, in one short paragraph.

**The purpose of this study is to evaluate the efficacy of the Aerodentis system for orthodontic tooth movement in an open label, two-arms, non-inferiority clinical study. This open label, two-arm study will follow 45 patients for up to fifteen (15) months. Thirty participants will wear the Aerodentis device, and fifteen participants will wear Invisalign. Patients will be assigned to participate in the treatment group using the Aerodentis device at home for 10 hours daily or in the control group using**

clear correctors for the duration of up to 15 months. Outcome assessments will be performed every 4 weeks. Assessments will include tooth movement and quality of life assessments.

#### **14. Background—in nontechnical, lay language**

Summarize in 2-3 paragraphs past experimental and/or clinical findings leading to the formulation of this study. Include any relevant past or current research by the Principal Investigator. For drug and device studies summarize the previous results (i.e., Phase I/II or III studies).

Dror Orthodesign is a medical device company that designs, develops, and manufactures pioneering orthodontic solutions to improve dental care and orthodontic treatment. The company's flagship Aerodentis system is an aesthetic alternative to conventional braces and clear aligners that is faster, more effective, safer and more comfortable.

The Aerodentis system is intended for the treatment of tooth malocclusion and is treated by applying force, over time, to teeth requiring alignment. Traditionally, the force has been created by attaching brackets to the teeth and creating tension through the stretching of flexible wire connected between the brackets. Alternatively, aligners are used for the treatment of tooth malocclusion. In these devices, a series of mouthpieces are used, where the force created by each mouthpiece on the treated teeth is designed to push the teeth in small, one step increments, toward the desired result. The Aerodentis system is an individually-fitted, plastic dental mouthpiece that is inserted and worn by the patient according to the dental practitioner's treatment plan. The Aerodentis system is comprised of a plastic mouthpiece containing an inflatable balloon that provides pressure (force) on the selected teeth designated to be moved to a final treated state. This allows patients complete freedom from orthodontic devices during the day. The inflatable balloon is inflated to the desired pressure using an electrical air pump unit that is programmed by the dental practitioner using Dror Orthodesign proprietary software; thus creating a course treatment specially designed for each patient.

The Aerodentis system was invented by [name], DMD, MSc, a specialist in orthodontics and dentofacial orthopedics and developed over seven years by a highly skilled team of engineers, orthodontics, industrial designers and dental technicians. The company is backed by a seasoned multidisciplinary team of executive professionals and researchers. Uniquely positioned to lead the market toward adopting this safe and effective platform, Dror Orthodesign is expanding the options for patients who can benefit from orthodontic treatment.

The Aerodentis system is CE-approved and is being used by doctors in Israel and Europe. CE marking on a product is a manufacturer's declaration that the product complies with the essential requirements of the relevant European health, safety and environmental protection legislation.

Dror Orthodesign is a privately held company with headquarters in Jerusalem, Israel. Dror Orthodesign has provided payment to Medistat for statistical services on this study.

#### **15. Participants (Screening and Selection)**

a. How many participants are to be enrolled at UAB? 45, 30 active and 15 control

If multi-center study, total number at all centers: \_\_\_\_\_

b. Describe the characteristics of anticipated or planned participants.

Sex: male and female

Race/Ethnicity: all races

Age: 12-60 with adult dentition (permanent teeth)

Health status: medically fit and well

*Note. If data from prior studies indicate differences between the genders or among racial/ethnic groups in the proposed research or if there are no data to support or to negate such differences, Phase 3 clinical trials will be required to include sufficient and appropriate entry of gender and racial/ethnic subgroups so that trends detected in the affected subgroups can be analyzed. If ethnic, racial, and gender estimates are not included in the protocol, a clear rationale must be provided for exclusion of this information. If prior evidence indicates that the results will not show gender or racial differences, researchers are not required to use gender or race/ethnicity as selection criteria for study participants. They are, however, encouraged to include these groups. See Section II. Policy of the NIH POLICY AND GUIDELINES ON THE INCLUSION OF WOMEN AND MINORITIES AS SUBJECTS IN CLINICAL RESEARCH – Amended, October, 2001) for further details.*

c. From what population(s) will the participants be derived?

**Incoming patients seeking orthodontic treatment**

Describe your ability to obtain access to the proposed population that will allow recruitment of the necessary number of participants:

**Patients will be screened by the orthodontic faculty members, Drs. [name], [name], and [name], at the orthodontic clinic**

Describe the inclusion/exclusion criteria:

**Inclusion:**

- 1. Permanent dentition**
- 2. Patients that in the opinion of the investigator will be compliant with device use. Compliance is determined by patient questionnaire.**
- 3. Class I malocclusion with crowding of  $\leq 6$  mm between the anterior teeth from the right first premolar to the left first premolar, on the upper and lower. Mild class II, class II subdivision.**
- 4. Good oral hygiene, as determined by investigator orthodontist.**

**Exclusion:**

- 1. Any medical or dental condition that, in the opinion of the investigator, could negatively affect study results during the expected length of the study. Conditions can include poor oral hygiene, extensive dental treatments, or periodontal disease.**
- 2. Patient is currently using any investigational drug or any other investigational device.**
- 3. Patient plans to relocate or move during the treatment period.**
- 4. Allergic to acetaminophen (use of aspirin or non-steroidal anti-inflammatory drugs is excluded for patients while on the study).**
- 5. Use of bisphosphonates (osteoporosis drugs) during the study.**
- 6. Pregnant females. Orthodontic treatment is not advised in pregnant females. Hormonal changes may affect tooth movement, the unborn fetus can be affected during mandatory x-rays, and unexpected complication in pregnancy may arise that could negatively affect orthodontic treatment.**
- 7. Patients that, in the opinion of the investigator orthodontist, are unable to comply with safe and effective device use.**
- 8. Patients that are likely unwilling to be compliant with device use, as determined by the questionnaire for compliance.**

d. If participants will comprise more than one group or stratification, describe each group (e.g., treatment/intervention, placebo, controls, sham treatment) **and** provide the number of participants anticipated in each group.

**This is an open label, two-arm, non-inferiority study. Patients will be systematically assigned to a treatment group (wearing the Aerodentis device) or control group (wearing clear aligners).**

Participants from the control group come from both current patients treated on site and new patients coming into the orthodontics clinics, requesting treatment with clear aligners.

- e. Indicate which, if any, of the special populations listed below will be involved in the protocol. Include the Special Populations Review Form (SPRF) if indicated.
- Pregnant Women: Attach [SPRF—Pregnant Women, Fetuses, Neonates/Nonviable Neonates](#)
  - Fetuses: Attach [SPRF—Pregnant Women, Fetuses, Neonates/Nonviable Neonates](#)
  - Neonates/Nonviable Neonates: [SPRF—Pregnant Women, Fetuses, Neonates/Nonviable Neonates](#)
  - Prisoners: Attach [SPRF—Prisoners](#)
  - Minors (<18 years old): Attach [SPRF—Minors](#)
  - Employees or students at institution where research conducted
  - Persons who are temporarily decisionally impaired
  - Persons who are permanently decisionally impaired (e.g., mentally retarded)
  - Non-English Speakers

**For each box checked**, describe why the group is included **and** the additional protections provided to protect the rights and welfare of these participants who are vulnerable to coercion: During the consent process, participants will neither be encouraged nor discouraged to be involved with the trial. Participants will be fully informed of the risks, benefits, and alternatives to participating in the trial. Also, they will be allowed to withdraw from the trial at any time. Students will be notified that their class standing and grades at UAB will not be affected. Students will not be offered or receive any special consideration when taking part in the research study. Employees will be notified that taking part in the study is not a part of UAB duties and refusing participation will not affect their job or relationship with UAB. Employees will not be offered or receive any special consideration when taking part in the study.

- f. List any persons other than those directly involved in the study who will be at risk. If none, enter "None": None
- g. Describe the process (e.g., recruitment, chart review) that will be used to seek potential participants (e.g., individuals, records, specimens). Research recruitment by non-treating physicians/staff may require completion of Partial Waiver of Authorization for Recruitment/Screening. (See <http://main.uab.edu/show.asp?durki=61981>.)  
Patients coming into the UAB orthodontic clinic, seeking treatment, will be screened by either [name], [name], or [name]. If the patients meet initial inclusion criteria during the screening process, the patient will be told about the study, and ask to fill out a questionnaire to determine if the patient is a good fit, and will be compliant throughout the study. Patients who are approved, will be consented on the Aerodentis study. Those who are not approved to wear the Aerodentis device, will be offered standard orthodontic care.
- h. If you will use recruitment materials (e.g., advertisements, flyers, letters) to reach potential participants, attach a copy of each item. If not, identify the source (e.g., databases) from which you will recruit participants.  
Flyers will be used as well as clinic patients.
- i. Describe the procedures for screening potential participants.  
All orthodontic patients who meet the inclusion criteria will be invited to participate.

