## 18. Risks

- a. List the known risks—physical, psychological, social, economic, and/or legal—that participants may encounter as a result of procedures required in this protocol. Do not list risks resulting from standard-of-care procedures. *Note. Risks included in this protocol document should be included in the written consent document.*

- Gums, cheeks, or lips may be irritated by mouthpiece.
- Failure to wear the appliance for the required treatment time and/or not using the product as directed by your doctor can lengthen the treatment time and affect the ability to achieve the desired results.

b. Estimate the frequency, severity, and reversibility of each risk listed.

Mild, when wearing device. Patient may stop wearing device if risks occur.

c. Is this a therapeutic study or intervention?

Yes No

**If Yes**, complete the following items:

i. Describe the standard of care in the setting where the research will be conducted: The most common standard of care for orthodontic movement of teeth in correcting malocclusion is by providing mechanical forces, involving a system of metal archwires and brackets, typically referred to as orthodontics, and known to many as "braces". The basic system is augmented with elastics, metal bands, headgear, retainers, and other ancillary devices as dictated by the specific treatment. These forces are static in that they are only adjusted at specific visits but then stay constant and do not change between visits.

ii. Describe any other alternative treatments or interventions: Participants may choose not to participate in the Aerodentis clinical trial and continue receiving routine orthodontic treatment at UAB's Department of Orthodontics.

iii. Describe any withholding of, delay in, or washout period for standard of care or alternative treatment that participants may be currently using: N/A

d. Do you foresee that participants might need additional medical or psychological resources as a result of the research procedures/interventions? Yes No

**If Yes**, describe the provisions that have been made to make these resources available.

\_\_\_\_\_

e. Do the benefits or knowledge to be gained outweigh the risks to participants?

Yes No

**If No**, provide justification for performing the research: \_\_\_\_\_

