Statistical Analysis Plan

Title of Research: Aerodentis Clinical Trial: Assessment of the Efficacy of

Orthodontic Tooth Movement Using the Aerodentis System

UAB IRB Protocol #: F160418007

Principal Investigator: [name] [name], BDS, MScD, PhD.

Co-investigators: [name], DMD, PhD

[name], DDS

Sponsor: Dror Orthodesign Ltd.

[name]

[name]

[name]

Statistical Considerations

Overview and Rationale for Primary Parameter

The aims of this trial are to assess the safety and efficacy of the Aerodentis system in producing tooth movement. Safety is measured by absence of root resorption while efficacy is typically measured by various parameters relating to tooth movement. Because tooth movement is highly variable between individuals, treatment success is not usually contingent on a specific amount of movement over time. To this end we specify the primary endpoint, achieving score <1mm in Little's index

Design

Historical controls will be utilized as a comparator group. This historical data will be generated using the same inclusion/exclusion criteria as the proposed prospective single arm study. The historical patient population will be derived from the study sites participating in this prospective study. The study inclusion/exclusion criteria will be applied to consecutive patients treated with clear correctors that have the potential for complete datasets (as defined by the study protocol).

The use of single arm, open label trial with historical controls is supported when a device technology is well developed and the subject of interest is well understood^[1]. Orthodontic treatment of this patient population (i.e., use of mechanical force) is well developed and understood. In addition, the primary

Page 1 of 3

Version Date: 9/27/2016

^[1] Draft Guidance for Industry, Clinical Investigators, and Food and Drug Administration Staff Design Considerations for Pivotal Clinical Investigations for Medical Devices, published August 15, 2011.

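### Two compliance criteria rest on a research-only questionnaire that historical and already-treated aligner controls cannot have taken before treatment, so the groups may not be selected alike.

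*Protocol*

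**What the plan says.** **Compliance criteria.** Protocol item 15.c, inclusion 2, admits "Patients that in the opinion of the investigator will be compliant with device use" and names a patient questionnaire as the means of judging this. Exclusion 8 removes "Patients that are likely unwilling to be compliant with device use, as determined by the questionnaire for compliance". Both are listed once for the whole study, not by arm. Exclusion 7 also concerns compliance, but rests on the orthodontist's opinion and does not mention the questionnaire. The procedure table in item 16.e shows the questionnaire as done once, taking 10 minutes, and as research rather than routine care.

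**Consequence of the screen.** Item 15.g says the form is used "to determine if the patient is a good fit, and will be compliant throughout the study". It then says "Patients who are approved, will be consented on the Aerodentis study", and of the others, "Those who are not approved to wear the Aerodentis device, will be offered standard orthodontic care".

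**Source of controls.** Three accounts are given:
- Item 16.a: an eligible pool is formed first, and participants are then randomly selected for one of the two groups.
- Item 15.d: assignment is systematic, and "Participants from the control group come from both current patients treated on site and new patients" who ask for clear aligners.
- SAP, Design: the comparator is historical, drawn from consecutive patients treated with clear correctors. The SAP states: "This historical data will be generated using the same inclusion/exclusion criteria as the proposed prospective single arm study".

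**The concern.** Both appliances are removable, so results depend on wear. Item 18.a lists failure to wear the appliance among the risks because it can prolong treatment and affect the result. A screen that predicts wear is therefore likely to predict success.

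If Aerodentis patients pass such a screen and some controls never faced it, the groups differ at baseline on a factor related to outcome. In a study described as non-inferiority, an artificially low control success rate makes the new device look better than it is and makes a false claim easier to reach.

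The SAP's closing promise to assess the effects of noncompliance would not repair this. No method is given, and item 16.a mentions a check of regular use only for the Aerodentis device. The refunds in item 16.h that depend on wear also go to the Aerodentis group only, which would add to any imbalance.

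**Working it through.** **Step 1. Which controls could have taken the questionnaire before treatment?**

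| Control source | Where stated | Questionnaire before treatment? |
|---|---|---|
| Random selection from an eligible pool | Item 16.a | Yes, if the pool applies all of item 15.c |
| New patients requesting aligners | Item 15.d | Possible; item 15.g screens patients seeking treatment |
| Current patients who began before the study | Item 15.d | No; the form is not part of routine care |
| Historical aligner patients | SAP, Design | No, for the same reason |

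For the last two rows, inclusion 2 and exclusion 8 cannot be applied as written. Neither document gives a substitute, such as a judgement from records. This does not depend on how item 15.g is read.

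**Step 2. Is there a figure in the plan to reproduce?** No. The protocol's arms add up (30 + 15 = 45), and the SAP plans 40, all in the tested group. Neither document gives a margin, a power, an expected success rate or a share of patients expected to fail the screen. What follows is illustration only.

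**Step 3. Size of the bias under assumptions.** Let pc be success in likely compliers, pn success in likely non-compliers, and q the share of likely non-compliers among all controls. The appliances are taken as equally effective and the Aerodentis arm as fully screened.

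- Control success = (1 − q) × pc + q × pn
- Bias in favour of Aerodentis = q × (pc − pn)

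With pc = 0.80 assumed, each cell shows control success and bias:

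| q | pn = 0.60 | pn = 0.40 | pn = 0.20 |
|---|---|---|---|
| 10% | 0.78; 2 points | 0.76; 4 points | 0.74; 6 points |
| 20% | 0.76; 4 points | 0.72; 8 points | 0.68; 12 points |
| 30% | 0.74; 6 points | 0.68; 12 points | 0.62; 18 points |

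Example: q = 20% and pn = 0.40 give 0.8 × 0.80 + 0.2 × 0.40 = 0.72, so the bias is 0.80 − 0.72 = 0.08. If only some controls are unscreened, q and the bias shrink in proportion.

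**Step 4. Effect on a non-inferiority conclusion.** Assume a margin of 20 points, 30 against 15 patients, and a claim when the lower limit of the two-sided 95% Wald interval for the difference lies above −0.20. Set Aerodentis truly worse by exactly the margin among likely compliers (0.60 against 0.80). Summing exact binomial probabilities gives the chance of a false claim:

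| Bias (points) | Observed control rate | Chance of a false claim |
|---|---|---|
| 0 | 0.80 | 0.0225 |
| 2 | 0.78 | 0.0317 |
| 4 | 0.76 | 0.0434 |
| 8 | 0.72 | 0.0753 |
| 12 | 0.68 | 0.1199 |
| 18 | 0.62 | 0.2128 |

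If both groups pass the same screen before allocation, q is 0 by design and this source of bias disappears.

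**The case against.** The strongest reply is that the plan already screens both arms. The criteria are study-wide and the questionnaire concerns compliance throughout the study. Item 16.a places random selection after the pool is formed, and the table in item 16.e lists questionnaire, photo review and consent ahead of fitting either appliance. The Aerodentis study may simply be the trial's name, and item 14 itself refers to aligners as devices.

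This defeats one tempting inference, that the screen acts solely as a gate to Aerodentis. It does not remove the problem. Items 15.d and 16.a and the SAP cannot all describe the same controls, and two of the three accounts admit patients who could not have been screened.

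A reader might also infer that patients who fail the questionnaire are passed into the control arm. The text does not say so. They are offered standard care, which item 18.c.i describes mainly as brackets and archwires, and exclusion 8 still applies to them. A rejected patient could choose aligners and later count as a current patient, but that is a gap in the wording and not a plan.

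Three further replies carry weight. The SAP limits historical controls to patients with potentially complete data, which may favour attenders and completers and so push the other way. The questionnaire is an attachment not available here, so its exact scope is unknown. The SAP states no margin, and its hypothesis is a Little's index threshold rather than a comparison of groups, so the error rates above belong to an assumed test.

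**Conclusion.** The point holds in a conditional form. It is certain from the text that the three accounts of the control group conflict. It is also certain that the SAP's statement of identical eligibility cannot be met for inclusion 2 and exclusion 8 in historical patients, or in current patients who began treatment before the study.

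Whether bias follows depends on which control source is used. If it is the randomised pool with the full criteria applied, this source contributes none. If current or historical patients are used, Aerodentis patients are selected for expected compliance and those controls are not. That would probably favour Aerodentis, provided that predicted compliers do better.

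The size is unknown. The 2 to 18 points, and the rise in false claims from about 2% to between 3% and 21%, rest wholly on assumed success rates, non-complier shares and margin. Neither the amount nor the net direction should be treated as established, because the complete-data condition may offset part of the effect.

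**What to change.** 1. Reconcile protocol items 15.d and 16.a and the SAP Design section to one control source and one allocation method. The other changes depend on this.
2. In item 15.c, word the compliance criteria for either removable appliance. In item 15.g, have every prospective candidate complete the questionnaire and be accepted before the group is known, and state that a patient rejected on it enters neither group.
3. In the SAP Design section, correct the statement of identical criteria. If current or historical controls are kept, pre-specify a compliance criterion judged from records by someone blind to outcome, say plainly that it is not equivalent to the questionnaire, and add a sensitivity analysis for the difference.

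The cost is a 10-minute form for each prospective control candidate, some record review if existing patients are used, and a less favourable statement of comparability. Excluding every control without a questionnaire would be stricter, but it would remove the SAP's whole historical comparator. That is a redesign rather than a change of wording, and it is not proposed here.
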